Presentation of cocaine-paired cues elicits a stress response in cocaine-dependent individuals. Neuroimaging studies indicate substantial overlap in the corticostriatal limbic circuitry responsible for cue and stress-primed drug craving. Oxytocin receptors have been localized to these same regions and preclinical studies have shown that oxytocin attenuates the acute reinforcing properties of psychostimulants. Despite these findings, little is known about the role of oxytocin in modulating the affective response to cocaine-paired cues and associated neural activity in cocaine-dependent men and women and whether there are gender differences in this modulation.

**Hypothesis 2a:** Intranasal administration of oxytocin will decrease subjective ratings of cue-induced cocaine craving in cocaine-dependent men and women compared to placebo administration.

**Hypothesis 2b:** Intranasal administration of oxytocin will decrease functional activity in the anterior cingulate cortex, amygdala, striatum, and prefrontal cortex compared to placebo administration.

**Exploratory Hypothesis 2c:** The attenuation of functional activity in the anterior cingulate cortex, amygdala, striatum and prefrontal cortex following oxytocin administration will be greater in cocaine-dependent women as compared to cocaine-dependent men.

**Exploratory Hypothesis 2d:** Oxytocin will modulate resting-state and task-related functional connectivity among sub-networks implicated in reward and motivation (nucleus accumbens, and orbitofrontal cortex),

memory and learning (amygdala and hippocampus), and cognitive control (prefrontal cortex and anterior cingulate cortex). Oxytocin may increase connectivity between reward/motivation and cognitive control sub-networks in craving states as an index of top-down regulation.

**In summary**, the proposed project will provide important data on the effect of oxytocin on stress and craving in cocaine-dependent individuals, explore the neural circuitry involved in response to oxytocin administration, and investigate whether sex/gender differences in response exist.

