3. Scanning Procedures. Prior to entering the scanner, subjective measures, physiologic measures (heart rate and blood pressure) and salivary cortisol will be collected. Participants will be given earplugs/headphones to protect their hearing and an optical hand pad rating device to allow them to respond to study tasks. Their ability to view a nearby projection screen (via a back-projected mirror mounted to their head coil) and correctly make ratings with the hand pad will be assessed prior to scanning. During initial scanner tuning, localizing, and structural scanning, participants will be shown relaxation images (i.e., 20 scenic pictures, each displayed for 30 seconds). Next participants will be asked to look at a cross-hair for 6-minutes while resting state connectivity data are collected. Next, the cocaine cue exposure paradigm will be administered. The paradigm to be used was adapted from a well-studied alcohol-cue exposure paradigm (George et al., 2001; Myrick et al., 2008), and is currently being utilized in an ongoing imaging study being conducted by the research team (R01DA023188-S1; PI: [name]; see Preliminary Data). The paradigm consists of pictures of cocaine and related objects (e.g., crack pipe), neutral objects (e.g., furniture), and visual control images that match the cocaine pictures in color and hue, but lack object recognition. Stimulus presentation occurs over six 90-second epochs. Each epoch contains three 24-second blocks (cocaine images, neutral objects, control images), containing five pictures displayed for 4.8 seconds each, and one 24 second rest block (i.e., cross-hair). Blocks, and stimuli within blocks, are presented in pseudorandom order. During the task, participants will be asked to rate their stress and craving after each block using their hand pad; ratings range from zero (“none”) to four (“severe”). Salivary cortisol and subjective measures will be collected immediately following the task, and 30 and 60 minutes post task.

4. Discharge. Following data collection, the participants will be debriefed, and scheduled for follow-up appointments. As on Day 1, a member of the research staff will be available to discuss management of any craving urges if craving remains elevated at the end of study procedures.

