(SPM 8, The Wellcome Department of Cognitive Neurology, London). All volumes within a task run will be realigned to the first volume. After realignment (including adjustment for sampling errors), scans with greater than one mm in three axes or one degree in three orientations will be excluded from group analyses. Following realignment, images will be stereotactically normalized into a standard space with a resolution of 2x2x2 mm voxels using the Montreal Neurological Institute (MNI) EPI template in SPM8. Subsequently, the data will be smoothed with a 8x8x8 mm Gaussian kernel and will be high-pass filtered (cue exposure paradigm cut-off period = 288s). Following preprocessing, within-task data from individual participants will be analyzed with a fixed-effects general linear model (GLM), with cocaine cue exposure activity modeled as a box-car function convolved with the standard canonical hemodynamic response function. The GLM procedure is repeated for each voxel with six movement parameters (3 rotation values in radian and 3 translation values in millimeter) included as covariates to control for the influence of head motion on the data. First-level analysis will be conducted and contrast maps will be generated. For the cue exposure paradigm, the main contrast of interest is the cocaine pictures vs. neutral objects contrast. Following first-level analysis, subject-specific contrasts will be entered into second-level, random-effects analyses. Areas of brain associated with group (oxytocin vs. placebo) and sex (women vs. men) differences on these contrasts will be identified using independent samples t-tests within a GLM framework. The combined group parameter maps will be threshold using a significance level of  $p < 0.05$ , corrected for multiple comparisons.

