For Exploratory Hypothesis 2d, a graph-theory approach to functional connectivity will be used. The BCT (Rubinov & [name], 2011) includes metrics specifically designed for functional brain networks, which are fully connected with weighted and signed connections. The metrics combine both positive and negative weights, but weight the positive connections more heavily. Within each of 116 anatomical regions of the AAL atlas, the average intensity value at each time point will be extracted for each subject. The time series (shifted by one TR) will be segmented into four separate time series, one for each condition (cocaine images, blur, objects, rest) (Fair et al., 2007; Just et al., 2004). Correlation matrices will then be computed for each subject and each condition and submitted to the BCT. For each subject and each condition, several BCT metrics will be computed (see Rubinov & [name], 2011 for more details). Network measures include *modularity* and *number of modules*. Node-specific measures include *diversity coefficient*, *within-module weights*, *within-module clustering coefficient*, and *strength*. We will also compute 20 random networks for each subject that preserve the weight and strength properties of the cocaine network (following Rubinov & [name], 2011), since that is the network of most interest. The same metrics that are computed for the cocaine, object, blur, and rest networks will be computed for the 20 random networks, then averaged to provide a single metric for the random network. In addition, a group-average correlation matrix will be computed (Pearson r-values from individual participants are Fisher z-transformed prior to averaging) for each of the four conditions and subject groups to obtain a modularity partition for the group, which will be visualized using Gephi software (Bastian, Heymann, & Jacomy, 2009), as in Figure 4. Network and node-based metrics will be submitted to mixed ANOVAs (one ANOVA for each metric and each node in the case of node-based metrics) with gender and treatment as between-subjects variables and condition (cocaine, object, blur, rest, random) as the repeated factor. Most metrics allow for comparison with the random networks except for strength and weight metrics because those are preserved in random networks and will be identical to the cocaine condition.

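### Exploratory Hypothesis 2d: the task-segment correlations keep the cue-evoked response, so a fall in activation can appear as a fall in connectivity

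*Combined protocol and SAP*

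**What the plan says.** Section C.2.d describes two analyses of the same cue run.

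- **Activation (Hypothesis 2b).** The first-level model has "cocaine cue exposure activity modeled as a box-car function convolved with the standard canonical hemodynamic response function". It is used to build contrast maps. Nothing says that its residuals go anywhere else. The high-pass cut-off for the cue run is 288 s.
- **Connectivity (Hypothesis 2d).** Within each atlas region, "the average intensity value at each time point will be extracted for each subject". Then "The time series (shifted by one TR) will be segmented into four separate time series, one for each condition", and "Correlation matrices will then be computed for each subject and each condition and submitted to the BCT". The graph metrics go to mixed ANOVAs with gender and treatment between subjects and condition repeated.

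The Specific Aims predict for 2b that "Intranasal administration of oxytocin will decrease functional activity in the anterior cingulate cortex, amygdala, striatum, and prefrontal cortex" compared with placebo, and for 2d that "Oxytocin will modulate resting-state and task-related functional connectivity among sub-networks". The 2d nodes include the amygdala, prefrontal cortex, anterior cingulate and nucleus accumbens, so the two hypotheses share regions. For 2d the aims add that oxytocin may raise connectivity between the reward/motivation and cognitive control sub-networks.

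**The concern.** Cutting a series by condition and correlating within the cut removes the segment mean. It does not remove the rise and fall of the evoked response inside each block. That movement is common to every region that responds to the cues, and it scales with the size of the response. The correlation therefore mixes coupling with co-activation.

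If 2b is right and oxytocin lowers activation, correlations between co-activated regions can fall even when coupling does not change. A 2d result could then partly restate 2b. A true rise in reward/control connectivity could be hidden or appear as a fall. The same mechanism can produce condition or sex effects wherever activation differs by condition or sex.

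**Working it through.** The plan gives no figure for this point (no expected correlation, evoked amplitude or power for 2d), so there is none to reproduce.

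**Inputs from the documents.** TR is 2.5 s (Image Acquisition Parameters), so one TR is a 2.5 s shift. From Scanning Procedures: "Stimulus presentation occurs over six 90-second epochs", and "Each epoch contains three 24-second blocks (cocaine images, neutral objects, control images", plus a 24 s rest block. Volumes per condition: 6 × 24 / 2.5 = 57.6. The power section gives 60 completers per group. Four 24 s blocks make 96 s against the stated 90 s epoch, and a rating follows each block, so the gap between blocks is uncertain; 0 to 6 s was used.

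**Assumptions.** Double-gamma response; evoked plateau A in units of regional noise SD; oxytocin cuts A by 30% or 50%; coupling identical in both arms; two-sided alpha 0.05.

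**Step 1: does the filter remove the response?** No. A 288 s cut-off passes anything faster, including responses to 24 s blocks.

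**Step 2: variance left inside a segment.** Let v be the within-segment variance of the unit evoked response in the cocaine segments.

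- One-TR shift: 0.03 to 0.08 with back-to-back blocks, 0.11 to 0.12 with a 6 s gap.
- Two-TR shift: 0.01 to 0.04.

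A longer shift shrinks v but does not bring it to zero.

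**Step 3: effect on a correlation.** Take two regions with unit noise variance, background correlation rho and equal plateau A. The covariance is rho + A²v and each variance is 1 + A²v, so

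r = (rho + A²v) / (1 + A²v).

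With rho = 0.30 and activation halved:

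- A = 1, v = 0.08: 0.38/1.08 = 0.352 falls to 0.32/1.02 = 0.314.
- A = 1, v = 0.11: 0.41/1.11 = 0.369 falls to 0.3275/1.0275 = 0.319.
- A = 0.5: the fall is 0.010 (v = 0.08) to 0.014 (v = 0.11).
- A = 0.25: the fall is under 0.01.

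If only one region responds, r = rho/√(1 + A²v). At A = 1 and v = 0.11, 0.30/√1.11 = 0.285 moves to 0.30/√1.0275 = 0.296, which is small and in the other direction.

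**Step 4: false rejection under the planned between-subjects test.** Mean Fisher z among 10 co-activated regions, 60 per group, range over gaps of 0 to 6 s:

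| Amplitude, cut | One-TR shift | Two-TR shift |
|---|---|---|
| 0.5 SD, 50% | 0.07–0.11 | 0.05–0.07 |
| 1.0 SD, 30% | 0.21–0.63 | 0.06–0.13 |
| 1.0 SD, 50% | 0.29–0.89 | 0.06–0.19 |

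A run with background correlation 0.30 (between-person SD 0.15 on the z scale, AR(1) noise 0.3) gave 0.14 to 0.50 at one TR for 1 SD and a 50% cut. The overall range at 1 SD is therefore about 0.14 to 0.9. At 0.5 SD with a 30% cut, another run gave about 0.06. Node strength behaved like mean Fisher z. The cocaine-minus-object difference, the nearest analogue of the treatment-by-condition term, rejected in 3% to 21% of trials at 0.5 SD and 27% to 96% at 1 SD (50% cut, one TR).

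**Step 5: after regressing out the evoked responses.** Mean r stays at 0.30 to 0.31 in both arms, and rejection returns to roughly 0.05 to 0.09. This is a best case, because the fitted response shape equals the simulated one.

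**The case against.** **Much of the size belongs to the one-TR shift.** This stands. Under the planned between-subjects test, a two-TR shift leaves little at 0.5 SD and a modest excess at 1 SD. A within-person test would show more: about 0.15 and 0.24 at two TR for 1 SD with cuts of 30% and 50%. The plan does not specify such a test for 2d, so those figures should not be used as the headline.

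**Regions may not co-activate.** This stands in part. With five responsive and five non-responsive regions, mixed pairs rejected at about 0.05 up to 1 SD. The pilot activation list in C.1.c includes the anterior cingulate, right amygdala, right dorsolateral prefrontal and left orbitofrontal cortex, but not the striatum. C.1.d reports the caudate and putamen splitting off from the other modules in the cocaine condition, and the same network partition for blur as for rest. Pairs within the C.1.c list are exposed; accumbens pairs may be less so.

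**Connectivity is not defined as net of evoked co-fluctuation.** This also stands. Whether block-locked co-fluctuation counts as connectivity is partly a choice of estimand. A reader might infer that only residual effects may be called connectivity; the documents do not define the term that narrowly.

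**The cited segmentation papers may remove task responses.** One title concerns using blocked data to study resting-state connectivity. Its method is not in the documents, and the plan's own wording is mean intensity. The supportable statement is that no removal step is stated.

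**Conclusion.** The point holds in a limited form. Followed as written, the task-segment analysis for 2d does not separate coupling from co-activation. For pairs of cue-responsive regions, the activation drop predicted by 2b can pass for a drop in connectivity or hide a rise.

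The size rests on assumed amplitudes: negligible at about 0.25 SD or below, small at 0.5 SD, and potentially serious from about 1 SD at the one-TR shift. It was shown for mean Fisher z and node strength, not for modularity, diversity or the other planned metrics. It applies where both regions respond in the same direction; with opposite signs the shift reverses. If evoked and background signal shrink in proportion, r does not change.

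Two stronger readings are not supported. A reader might infer that the 2d test must reject whenever 2b is true; the results above, close to 0.05 in several settings, contradict that. A reader might also infer that all 2d connectivity results are affected. The separate 6-minute cross-hair run precedes the cues and carries no cue response, although C.2.d describes only the four task segments.

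Since 2d is exploratory, this is a cheap improvement and not a threat to the trial's main aims.

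**What to change.** In the 2d paragraph of C.2.d, before segmenting, regress each regional series on the cocaine, object and control-image regressors (box-cars convolved with the canonical response, as in the activation model). Compute the 2d correlation matrices and graph metrics from the residuals. Report the unresidualised matrices alongside, labelled as mixing co-activation with coupling. Where the two disagree, do not interpret the raw result as a change in coupling separate from activation. If residuals were intended all along, say so in the text.

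The cost is a short addition to the plan and one extra regression step, with no new data. The downside is that residualising also removes genuine coupling that is strictly time-locked to the blocks; the retained raw analysis still shows it.

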## PROTECTION OF HUMAN SUBJECTS

### 1. RISKS TO THE SUBJECTS

#### a. Human Subjects Involvement and Characteristics

Admission into the study is open to men and women and to all racial and ethnic groups, age 18-65. 152 participants (76 cocaine-dependent women and 76 cocaine dependent men) will be recruited primarily through internet and newspaper advertisements. Inclusion/exclusion criteria that apply to all subjects are listed below:

#### 1) General Inclusion / Exclusion Criteria

##### Inclusion Criteria

1. Subjects must be able to provide informed consent and function at an intellectual level sufficient to allow accurate completion of all assessment instruments.
2. Subjects must meet DSM-IV criteria for current cocaine dependence (within the past three months). While individuals may also meet criteria for abuse of other substances, they must not meet criteria for dependence on any other substance (except nicotine) within the last 60 days. Alcohol has been known to affect HPA function (Adinoff et al., 1991), however to enhance recruitment efforts individuals with alcohol dependence or abuse will be included in the study if they do not require medically supervised detoxification. Also, due to the high comorbidity of cocaine and marijuana dependence, and limited evidence that marijuana use affects HPA function, subjects with marijuana dependence will be included.
3. Subjects must consent to remain abstinent from all drugs of abuse (except nicotine) for a three-day period immediately prior to the throughout study procedures.
4. Subjects must consent to random assignment.
5. Subjects must consent to participating in study procedures at the ASD and completion of two fMRI scans.

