the SCID-I/P (Sheehan & Lecrubier, 2003; Sheehan et al., 1998). **Structured Clinical Interview for DSM-IV (SCID-I/P)**: The SCID-P is a structured diagnostic interview that assesses each of the criteria for DSM-IV diagnoses. The alcohol and drug use disorder modules will be to thoroughly assess both current and lifetime diagnostic status for abuse and dependence. It has excellent inter-rater and test-retest reliability (First et al., 2002). **Menstrual History Diary**: Participants will be asked to estimate the timing of their cycle for the 90-days prior to study entry and to track their cycle during study participation. **Daily Hassles Scale**: The Daily Hassles Scale consists of a list of 117 irritating, frustrating, or distressing events that characterize everyday interactions with the environment. Participants rate both frequency and intensity for the past month. The Daily Hassles Scale is positively correlated with adaptational ability and is a good predictor of psychological symptoms (Kanner et al., 1981). **Adverse Childhood Experiences (ACE) Questionnaire**: The modified ACE questionnaire assesses childhood maltreatment and exposure to household dysfunction. It has been utilized to examine the relationship between adverse childhood experiences and health risk behavior in adulthood (Felitti et al., 1998). In addition to providing data to assess the impact of early childhood trauma on cocaine use, utilization of the ACE will allow for potential cross-SCOR collaborations as it also being employed by the UCLA, Yale and Harvard SCORs. **Childhood Trauma Questionnaire (CTQ)**: The CTQ is a 25-item self-report questionnaire used to assess the extent to which individuals have experienced five domains of childhood abuse and neglect (sexual abuse, physical abuse, emotional abuse, emotional neglect and physical neglect). Subjects answer each question using a 5-point Likert scale ranging from (1) never true to 5 (very often true). Severity scores for each domain can range from 5 (no history of abuse/neglect) to 25 (severe abuse/neglect). The questionnaire also includes a minimization/denial scale. The reliability and validity of the CTQ are excellent (D. P. Bernstein, et al., 1997; D. P. Bernstein, Fink, L.A., 1998). The **Pittsburg Sleep Quality Index** will be used to assess sleep patterns (Buysse, et al., 1989). The **Quick Inventory of Depressive Symptoms** (Rush, et al., 2003) will be used to measure depression and a short form anxiety scale from the PROMIS© item bank will be used to measure anxiety. The **Life Events Occurrence Scale** (Maciejewski, et al.) will be used to inventory adult trauma. A brief survey from the National Health and Nutrition Examination Survey (CDC, 2000) will be used to rate quality of life, and a body map will be used to rate areas of pain. A brief smoking history will also be obtained.

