1. Medication Administration. Participants will be administered 40 IUs of oxytocin nasal spray or matching placebo at 40 minutes prior to study tasks. This dose was selected based on previous studies that have used similar doses of oxytocin (Ditzen et al., 2009; Heinrichs et al., 2003; Kubzansky et al., 2009), as well as our own previous pilot work (see Preliminary Data). Timing of administration is also based on our pilot work and previous studies showing central activity of oxytocin 40 minutes after intranasal administration (Heinrichs et al., 2009). Intranasal oxytocin and matching placebo will be compounded by a MUSC Investigational Drug Service. Randomization will be done by the MUSC Investigational Drug Service, who will keep a record of the blind and be available should unblinding be required. To achieve balance in sample size with respect to gender, a block randomized design with randomly varying block sizes will be used.

2. TSST. The TSST is a standardized psychological stress challenge which has been used extensively in research studies. A meta-analysis supports its utility for evoking a HPA axis stress response in a laboratory setting (Dickerson & Kemeny, 2004). It has induced a robust and reliable physiological stress response in cocaine, marijuana, and alcohol-dependent individuals in our previous studies (McRae et al., 2006; [name] et al., 2011; Waldrop et al., 2010). When the TSST begins, The participant will be told that (s)he will give a speech and perform an arithmetic task. The topic of the speech will be why (s)he should be hired for a particular job (the individual's "dream job"). The participant will deliver the speech as though speaking to a group of potential employers. The experimenter then tells the participant that (s)he has 5 minutes to prepare the speech, and starts the countdown clock (placed in view of the individual). The experimenter leaves the room to allow the participant to prepare. After 5 minutes, three individuals unfamiliar to the participant (the audience) enter the room and are seated; the individual will be instructed by one audience member to stand

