**C.2.d. Statistical Methods.** The hypotheses associated with Aim 1 are interested in the effect of oxytocin on cocaine craving and stress in response to the TSST. It is hypothesized that cocaine-dependent participants receiving oxytocin will demonstrate greater attenuation of stress and craving response to TSST as compared to those receiving matched placebo. A linear mixed effects model containing all serially measured time points will be used to assess the effects of oxytocin versus placebo on each dependent variable. Restricted maximum likelihood (REML; Patterson and Thompson, 1971) methods will be used to estimate the fixed effects and variance components, and baseline values will be used as covariates in the regression models. To test the hypothesis that women will experience greater ameliorative effects of oxytocin on stress and craving response following the TSST as compared to males, similar models will examine the differential (interaction) in the scores reported between men and women by treatment group (oxytocin vs. placebo). Additionally, as an exploratory analysis, the strength of the effects of oxytocin in women will be assessed with differences in estrogen and menstrual cycle phase as independent variables. In a subgroup analysis of women entered into the study, linear mixed effects models will be developed to assess the association of estrogen and menstrual phase (independently) on the stress and craving response to the TSST. Non-linear associations will also be explored using cubic spline models (Marrie et al., 2009). Within each family of dependent measures, the Type I error rate will be controlled using a post-hoc Bonferroni correction.

The hypotheses associated with Aim 2 are concerned with the impact of oxytocin on cocaine cue reactivity. It is hypothesized that oxytocin will decrease cue-induced cocaine craving in cocaine-dependent men and women compared with placebo administration. Post-acquisition preprocessing and statistical analysis will be performed using Matlab 7.8 (Mathworks, Sherborn, MA) with Statistical Parametric Mapping software 8

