**c.2.f. Design Considerations.** *Choice of experimental groups.* Inclusion of control participants was considered; however, craving is a main outcome measure of the proposed study, and it would not be expected that control participants would have a craving response to either the TSST or cocaine cues. Therefore, it was agreed that resources in this project would be best spent on including sufficient numbers of participants with cocaine dependence, as a demonstrated reduction in craving with oxytocin in this population may have important clinical implications. *Potential modifiers of cerebral blood flow.* Sex differences in hematocrit levels and baseline cerebral blood flow may impact the BOLD signal (Kastrup et al., 1997; Levin, et al., 2001). However, the present group comparisons will be based on changes in activation relative to control conditions (e.g., cocaine versus object activation differences for oxytocin versus placebo); therefore, even if baseline levels of blood flow are different across groups, the present analyses rely on fractional changes in fMRI signal relative to control and baseline conditions. Abstinence from cocaine has been shown to alter regional cerebral blood flow (Kosten et al., 1998; Volkow et al., 1988). If any statistical group differences are found, abstinence (days since last use) will be included as a covariate in the analysis.

**c.2.g. Operational Plan and Research Timetable.** The first three months of the grant period will be used to obtain regulatory approvals and database creation. Fortunately, because we have ongoing trials involving cocaine-dependent populations, we have trained personnel and an active recruitment network. We also have an active IND for use of oxytocin in cocaine-dependent individuals. We anticipate no issues with study recruitment beginning by the fourth month of the first year, and for a total of 51 months. At a recruitment rate of approximately three participants per month, we should have no difficulty in completing the study in this timeframe. Data analysis and manuscript preparation will take place during the last six months of the fifth year.

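### The protocol names alcohol as an influence on HPA function, admits alcohol-dependent participants and records the diagnosis, but leaves it out of the Aim 1 models and so gives up some precision, chiefly for cortisol

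*Combined protocol and SAP*

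**What the plan says.** Inclusion criterion 2 says "Alcohol has been known to affect HPA function" and then, to help recruitment, that "individuals with alcohol dependence or abuse will be included in the study if they do not require medically supervised detoxification". An earlier sentence of the same item bars dependence on any other substance except nicotine. C.2.a (Participants) and exclusion criterion 18 agree with the later sentence, so I read alcohol dependence as admitted, but item 2 should be reconciled with itself.

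The diagnosis is collected. Under Screening and Diagnostic Instruments (C.2.c.1.a), the SCID alcohol and drug modules are to "thoroughly assess both current and lifetime diagnostic status for abuse and dependence". Form 90 also tracks alcohol use.

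The analysis does not use it:

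- **Main models.** For the Aim 1 mixed models, C.2.d says "baseline values will be used as covariates in the regression models" and names no other covariate.
- **Hypothesis 1b.** For the sex comparison, "similar models will examine the differential (interaction) in the scores reported between men and women by treatment group", again with no alcohol term.
- **Randomisation.** The only balancing factor, under Medication Administration, is gender: "To achieve balance in sample size with respect to gender, a block randomized design with randomly varying block sizes will be used".
- **Other covariates.** Design Considerations (c.2.f) has one conditional rule: if groups differ, "abstinence (days since last use) will be included as a covariate in the analysis". That concerns cocaine abstinence and cerebral blood flow.

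**The concern.** Cortisol is an HPA measure and one of the trial's stress outcomes. A factor that the protocol itself says affects HPA function adds variance to that outcome when it is left in the residual. Randomisation keeps the oxytocin comparison fair, but it does not remove this variance.

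The baseline covariate may not cover all of it. The protocol does not say whether alcohol shifts resting levels, the response to a stressor, or both. Baseline adjustment absorbs a shift in resting level. It need not absorb a change in reactivity.

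A second, weaker issue concerns Hypothesis 1b. Sex is not randomised. If the oxytocin effect depends on alcohol dependence, and alcohol dependence is more common in one sex, part of an observed sex difference in the oxytocin effect would be due to alcohol. That matters for interpretation, because Specific Aims attributes the expected difference to estrogen.

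**Working it through.** **Inputs from C.2.e (Power and Sample Size).** Stress rating (VAS) d = 0.48; four post-task readings; ICC 0.78; design effect 3.35; type I error 0.05 (two-sided assumed, as the plan does not say); 120 completers; 80% power claimed for stress, and 80% for a 1 SD sex differential in the craving response.

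**Reproducing the plan.**

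- Per arm: 2 × (1.96 + 0.84)² / 0.48² gives 69 after rounding up, so 138 in total (stated 140).
- Completers: 140 × 3.35 / 4 = 117.25, hence 118, rounded to 120.
- Effective N at 120 completers: 120 × 4 / 3.35 = 143.3. Stress power is 81.9%, consistent with the stated 80%.
- Interaction at 30 per cell: SE = √(4/30) = 0.365 SD. Power for 1 SD is 78%, within two points of the stated 80%.

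None of these figures depends on alcohol adjustment.

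**Precision.** The documents give neither the alcohol-dependent share nor its effect on the response, so both are assumed. With share p = 0.5 and difference δ (in single-reading SDs), alcohol explains p(1 − p)δ² = 0.25δ² of single-reading variance. The variance of a participant's four-reading mean is (1 + 3 × 0.78)/4 = 0.835. Adjustment reduces it to 0.835 − 0.25δ². With 60 per arm, SE = √(2 × variance / 60) and power = Φ(0.48/SE − 1.96).

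| δ | Variance removed | Variance left | SE | Stress power |
|---|---|---|---|---|
| none | 0 | 0.835 | 0.167 | 82% |
| 0.3 | 0.0225 | 0.8125 | 0.165 | 83% |
| 0.5 | 0.0625 | 0.7725 | 0.160 | 85% |
| 0.7 | 0.1225 | 0.7125 | 0.154 | 88% |

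As a cross-check on another scale, suppose alcohol explains a further 1%, 5%, 10% or 20% of the participant-mean variance beyond baseline. Stress power then becomes 82.3%, 83.8%, 85.7% or 89.5%. Interaction power at 30 per cell moves from 78.2% to 78.6%, 80.2%, 82.3% or 86.5%.

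**Bias in the sex-by-oxytocin test.** The spurious interaction equals (difference in prevalence between sexes) × (change in oxytocin effect with alcohol dependence).

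- *Alcohol main effect only.* Simulation with 30 per cell, main effects of 0.5 or 1.0 SD with prevalences of 30% and 50% by sex, and of 0.5 SD with 20% and 60%: mean interaction about 0.00, rejection about 5%. No bias.
- *Both conditions, moderate.* A 20-point gap and modification of 0.3 to 0.7 SD give 0.06 to 0.14 SD, which is 0.16 to 0.38 of the 0.365 SE. Rejection rises from 5% to between 5.3% and 6.7%.
- *Both conditions, extreme.* A 40-point gap and 1.0 SD modification give 0.40 SD, with simulated rejection of about 17%.

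In that extreme case a main-effect alcohol covariate leaves the bias at 0.40 SD (19% rejection). Adding alcohol dependence-by-treatment removes it (0.00 SD, 5.1%).

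**Cost of the added interaction term.** Relative to the main-effect model, the sex-by-treatment SE grows by 1/√(1 − r²), where r² = 0.25 × gap² / [p̄(1 − p̄)] and p̄ is the mean prevalence. For 30% and 50%, r² = 0.042 and the SE grows 2%. For 20% and 60%, r² = 0.167 and it grows 10%.

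**The case against.** The strongest reply is that the premise supports little. The protocol says only that alcohol affects HPA function. A reader might infer that the sex-by-oxytocin test is therefore confounded, but that does not follow. Oxytocin is randomised, so within each sex alcohol dependence is independent of treatment in expectation, and a main effect of alcohol biases neither the treatment effect nor the interaction. Bias needs both a sex gap in prevalence and effect modification. The documents give no alcohol prevalence by sex and no direct evidence of modification. The nearest is the post-mortem finding of reduced hypothalamic oxytocin immunoreactivity in alcoholics, cited in Significance, which makes modification plausible but does not show it. This part of the reply stands.

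It also stands that the power figures above concern the subjective stress rating, because the plan gives no cortisol power; that the assumed inputs are not from the documents; and that whether the sex contrast should be conditional on alcohol status is a choice of estimand. The documents state no alcohol effect on craving. In Aim 2 each participant is scanned under both oxytocin and placebo, so a stable trait drops out of the within-person contrast unless it modifies the drug effect.

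The design controls answer less. Excluding people who need supervised detoxification, requiring three days of abstinence and breathalysing on test days limit severe cases and recent drinking. They do not remove differences due to dependence status.

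**Conclusion.** The point holds as a modest loss of precision. The plan names a factor that affects HPA function, admits people who have it, measures it, and then neither balances on it nor adjusts for it. The case is clearest for cortisol. For the stress rating the gain is about 1 to 6 power points, assuming half the sample is alcohol-dependent and differs by 0.3 to 0.7 SD. It is smaller to the extent that the baseline covariate already absorbs the difference. The true size cannot be found from the documents.

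The documents do not support calling the oxytocin effect biased or the Hypothesis 1b test confounded. The remaining risk is one of attribution and needs both conditions above. At a 20-point gap and 0.3 to 0.7 SD modification it is 0.06 to 0.14 SD, small against the planned 1 SD differential. It warrants a sensitivity analysis, not a change to the primary 1b model. This is a worthwhile refinement, not a flaw that threatens the trial's conclusions.

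**What to change.** In C.2.d, before unblinding, add current alcohol dependence (yes/no, from the structured interview) as a pre-specified covariate in the Aim 1 cortisol and stress models, and optionally in the craving model. Keep the primary Hypothesis 1b interaction as planned, and pre-specify a sensitivity analysis that adds alcohol dependence-by-treatment beside sex-by-treatment. A main-effect covariate alone would not address the attribution question. Report alcohol dependence by sex and arm so that readers can judge whether the sensitivity analysis matters.

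The cost is a sentence or two and one or two degrees of freedom, with no new data collection. In the sensitivity model the interaction SE is slightly wider: about 2% for a 20-point prevalence gap, and about 10% if the gap were as large as 40 points. Aim 2 needs no change.
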